6.6 Protection Against Risks

Risks to the participant will be minimized by thorough training and supervision of all staff. Participants' privacy will be assured by conducting interviews, surveys, and other forms of data collection in a private location, for example, in a private room at the health facility. The confidentiality of all study records will be safeguarded to the extent legally possible. All study data, reports, and administrative forms will be identified by a coded number only to maintain participant confidentiality. All databases will be secured with password-protected access systems, and computer entries will be identified by coded number only. Forms, lists, logbooks, appointment books, audio-recordings, and any other data forms that link participant ID numbers to other identifying information will be stored in a separate, locked cabinet. All data analysis will be done on transcripts which have only the study number as a unique identifier. Clinical information with individual identifiers will not be released without the written permission of the participant.

Participant name and contact information are the only individually identifiable private information that will be collected specifically for our project. Data will be entered into a protected electronic database and all analytic datasets will have only the study number as a unique identifier. Forms, logbooks, appointment books, and any other data forms that link participant ID numbers to other identifying information will be stored in a separate, locked file cabinet. Clinical information with individual identifiers will not be released without the written permission of the participant. Data collection forms, electronic databases, and printed data will only be supplied to appropriate study staff on an as-needed basis. Any publication about this research study will omit names and any other identifying information.

Paper copies of consent forms, observation forms, exit interviews, and surveys will be kept in a locked room at the UNC Project office in Lilongwe. Only staff and researchers directly involved in processing and analyzing data will have access and will be allowed to transfer the data to electronic databases. Voice recordings and electronic databases will be stored in computers with password protection. Any computers used will also be encrypted. Each participant will be assigned a unique identification number, which will be used in databases and on transcriptions instead of any identifying information. Paper copies and original voice recordings will be stored for 3 years after the completion of the publications from this research.

We expect these procedures to adequately protect participant confidentiality. However, it is possible that a participant's study participation could become known to people in the community and may result in stigma or discrimination. Should that occur, study staff will work

with the participant and their family as appropriate to resolve the situation in whatever manner is preferred. All study procedures carry minimal risks.

6.7 Potential Benefits of Proposed Research to Human Subjects and Others

Participants will not benefit personally from participating in this research. The results of this study may benefit society as the results can be used to develop a decision-making aid to help pregnant women, their partners, and clinicians make decisions about PrEP use. An improved decision-making process may lead to more appropriate and adherence PrEP use, which may ultimately serve to prevent HIV infection during pregnancy and mother-to-child transmission of HIV.

6.8 Inclusion of children, sub-populations, and vulnerable populations

This study focuses on the outcomes of pregnant and breastfeeding women; as such, they must be included in our study population. Prisoners will be excluded as they receive care at separate facilities.

6.9 Reimbursement/compensation

There is no cost to participate in the study. Participants will be provided with transport reimbursement for each study visit, according to local research standards.

6.10 Dissemination of findings

Study findings will be disseminated through appropriate local channels, including academic and public health research symposia. We will report findings to relevant local authorities in Malawi. One or more publications will also be submitted to a peer-reviewed journal. Our study team plans to publish the study results whether positive or negative. The study participants' privacy and confidentiality will be strictly maintained in all results dissemination or publication activities.

MI	Multiple Imputation
MyChoice	MyChoice for HIV Prevention Intervention
PrEP	Pre-exposure Prophylaxis
SAP	Statistical Analysis Plan
SD	Standard Deviation
SDM	Shared Decision Making
SOC	Standard of Care

3. Introduction

This statistical analysis plan (SAP) details the statistical procedures that address the study objectives specified in the September 2024 **protocol** of the investigator-initiated NIH-funded pilot study titled: **“Supporting oral pre-exposure prophylaxis decision making among pregnant women in Lilongwe, Malawi: a pilot study,”** also known as MyChoice Study 1.

The purpose of this pilot study is to evaluate the **feasibility, acceptability, and appropriateness** of a shared decision-making (SDM) intervention, **MyChoice**, designed to support HIV-negative

pregnant women in their decisions about initiating oral pre-exposure prophylaxis (PrEP). This SAP details the planned analyses for both the primary implementation outcomes and secondary cognitive outcome (decisional conflict), providing a framework for interpreting findings that will inform the design of a future efficacy trial.

4. Study Objectives and Summary

4.1 Protocol Title:

Supporting oral pre-exposure prophylaxis decision making among pregnant women in Lilongwe, Malawi: a pilot study

4.2 Study Design:

This study is a single-blind, pilot feasibility trial of the MyChoice shared decision making (SDM) intervention compared to standard of care (SOC) for pregnant women considering daily oral PrEP. We will evaluate the feasibility, acceptability, and appropriateness of the MyChoice intervention.

Population: The primary population for this study is pregnant women, aged 18 years or older, at risk of HIV infection that have not initiated PrEP. We focus on pregnant women because of the elevated HIV risk faced by women in the perinatal period.

Sample size: 100 participants in total, comprised of

- N=50 HIV negative pregnant women randomized to the MyChoice intervention arm
- N=50 HIV negative pregnant women randomized to the Standard of Care (SOC) arm

Follow-up: Participants will be followed for approximately three months from enrollment, with study visits at months 0, 1, 2, and 3 (see **Appendix A** for-visit windows).

Study site: Lilongwe, Malawi (Bwaila Hospital)

Study duration: The length of participant follow-up is approximately three months from enrollment (month 0).

Study groups: Participants randomly assigned to the *control group* will receive SOC HIV prevention counseling in accordance with the usual care in Malawi per national guidelines. Women randomly assigned to the MyChoice *intervention group* will receive the MyChoice study intervention, My Choice for HIV Prevention (MyChoice) counseling, a counselor-delivered shared decision-making approach for pregnant women considering PrEP.

Clinical Trial ID: NCT06394323, clinicaltrials.gov

4.3 Study Aims

Specific aims which will be completed through the pilot study are as follows:

Aim 1: Evaluate the acceptability, appropriateness, and feasibility of the MyChoice PrEP shared decision-making intervention.

Aim 2: Assess the plausibility of intervention effects on a proximal cognitive endpoint (decisional conflict) in preparation for a future efficacy trial.

4.4 Study Outcomes

We will assess the following primary and secondary outcomes in this feasibility pilot study.

4.4.1 Primary Outcomes

Primary outcomes will include participant-reported perceptions of the MyChoice intervention (assessed through questionnaire self-report using validated scales)¹:

- *Intervention acceptability:* the extent to which participants perceive the intervention to be agreeable, palatable, or satisfactory will be assessed using the Acceptability of the Intervention Measure (AIM) scale.¹
- *Intervention appropriateness:* the perceived relevance and usefulness to support decision making will be assessed using the Intervention Appropriateness Measure (IAM) scale.¹
- *Intervention feasibility:* the extent to which the intervention is feasible or practical will be assessed using the Feasibility of Intervention Measure (FIM) scale.¹

Primary study outcomes will be assessed through participant questionnaires at the enrollment visit among MyChoice arm participants. Acceptability and Appropriateness outcomes will also be assessed at the month 2 follow-up visit among MyChoice arm participants to understand how perceptions of the MyChoice intervention change over time.

4.4.2 Secondary Outcomes

The secondary outcome of decisional conflict will be assessed through participant self-report using a validated scale to assess the extent to which the counseling received by participants in either arm helped them make decisions about HIV prevention during pregnancy and breastfeeding.

Decisional conflict or perceptions regarding decision uncertainty, satisfaction, clarity of personal values, and support for decision-making will be assessed with the Decisional Conflict Scale.²⁻⁵

The secondary outcome will be assessed in the study questionnaire at the enrollment visit among all participants after receipt of study counseling.

5. Randomization and Masking Procedures

Once enrolled, at their first visit (month 0, expected to be the same date as screening), participants will be randomly assigned to one of two study arms (MyChoice or SOC) at a 1:1 study arm ratio. The randomization assignments will be generated in advance using a permuted block design. All

randomization plans, including a back-up randomization plan for replacement randomization ID (RID), will be generated using SAS version 9.4 (SAS Institute, Cary, NC). The treatment arm assignment, as linked to a RID, will be placed in opaque sealed envelopes and sequentially numbered with these RID.⁶ Once RID is assigned, the corresponding intervention (MyChoice or SOC) is administered as outlined in the protocol.

6. General Statistical Considerations

In this pilot study, the primary objective is to understand **acceptability**, **feasibility**, and **appropriateness** of the MyChoice intervention. Given the pilot nature of the study, emphasis will be placed on **estimation and precision** rather than hypothesis testing.

6.1 Descriptive Statistics

Initial analysis will include descriptive analyses to characterize the population on features such as demographics (e.g., age, marital status, income, education) and each outcome of interest. We will examine whether key sociodemographic features (including but not limited to: age, income, education, marital status, gestational age, perceived HIV risk, and experience of IPV) differ by study arm (n (%)) for categorical data and median (25th, 75th percentile), mean (SD), median (IQR) and min-max for continuous measures). Testing and confidence intervals (CIs) will be two-sided and at a 95% confidence level (i.e., alpha 0.05) with no adjustment for multiplicity, unless stated otherwise. Any characteristics differing significantly by arm may be included as covariates in all analyses comparing study arms.

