5.16 Data Analysis

Initial analysis will include descriptive analyses to characterize the sample on features such as demographics (e.g., age, marital status, income, education) and each outcome of interest. We will examine whether key sociodemographic features (age, income, education, marital status, gestational age, parity, perceived HIV risk, and experience of IPV) differ by study arm. Any characteristics differing significantly by arm will be included as covariates in sensitivity analyses comparing study arms; otherwise, primary analyses will be unadjusted

Given the pilot nature of the study, emphasis will be put on estimation and precision of measured effects, rather than null hypothesis testing. An alpha=0.05 will be used throughout to compute 95% confidence intervals (CIs), with no adjustment for multiplicity. In the case of small cell counts or analyses of continuous data with n<30, exact statistical methods (e.g., exact CI for a risk difference) will be used. Given potential for precision loss with exact CI methods and the pilot nature of these studies, we will use large-sample methods (e.g., Wald CIs) when the nominal CI coverage level is tenable.

Specific analyses for each study outcome are described in detail below. Detailed statistical analysis plans will be finalized prior to study outcome analysis.

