5.16.2 Analysis of secondary endpoints

Decisional Conflict

Decisional Conflict Scale (DCS) will be calculated according to published methods. A mean of the 16-item scale (rated on a 5-point scale) will be taken and multiplied by 25 to produce summary scores ranging from 0-100 points.^{71,74} Descriptively, summary scores will be presented descriptively (mean and SD across participants in each arm by study). We will compare DCS scores across in the SDM intervention condition to the SOC counselling control condition in an exploratory manner. We hypothesize that the intervention will be superior to the control, with intervention participants reporting at least an 8-point lower decisional conflict score on average than control participants. An intent-to-treat approach will be used to evaluate the effect of treatment on decisional conflict. We will first compare group means of decisional conflict scores by study arm and then examine the intervention's effect on this outcome using a two-sample Welch's t-test. If demographic variables related to decisional conflict differ substantively by study arm, we will instead use augmented inverse probability weights (AIPW) to perform doubly robust estimation of the average intervention effect to compare intervention vs. control (e.g., using the CAUSALTRT procedure in SAS software). Missing (unevaluable) data are anticipated to be uncommon ($\leq 10\%$). Multiple imputation methods will be applied to address missing data if appropriate.

Exploratory analyses will also be conducted with a dichotomous coding of DCS score according to published thresholds. A "low" DCS score will be identified using a cut-off of 25 out of 100, which has been linked to reduced decisional regret and enhanced choice retention. DCS scores will be computed based on women's responses to statements, where higher scores indicate greater decisional conflict, while lower scores indicate diminished conflict and heightened certainty in decision-making.

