6.6 Chance Imbalance

We anticipate that our measured baseline covariates will be balanced between the arms by randomization. However, if there is evidence of considerable chance imbalance in key baseline covariates, a **post hoc sensitivity analysis** may be conducted for the secondary outcome using **Augmented Inverse Probability Weighting (AIPW)** to adjust for these imbalances and can be used to produce double robust effect estimates compared to Inverse Probability of Treatment Weighting (IPTW). This analysis will be exploratory in nature and will not replace the unadjusted primary analysis. A doubly robust approach would also be suitable, if feasible, given our sample size (n=50 per arm). The protocol does not address chance imbalance, and such an analysis would be a sensitivity approach.

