8.5 Analysis

- (i) **Item-Level Summary:** We will describe the responses for each of the 16-items on the Decisional Conflict Scale (DCS) at **month 0**. Descriptive statistics will include counts, percentages, and graphical summaries, as appropriate.
- (ii) **Scale-Level Summary:** For each participant, in each study arm, we will calculate the mean of their completed DCS at **Month 0** and multiply that result by 25 to produce a standardized summary score ranging from 0 to 100, in accordance with the established scoring procedures. Only participants with at least one completed DCS item will be included in the analysis. For each study arm, we will calculate the mean of participants' individual summary scores (mean of means), the SD, and the 95% CI using the common variance.
- (iii) **Between-Group Comparisons:** We will compare the mean DCS scores between the intervention (MyChoice) and SOC arms using the Welch's t-test (assuming unequal variance). We will also report the absolute difference in mean scores between arms (SOC as the referent), along with the associated 95% CI using the pooled variance assumption.
- (iv) **Missing Data:** If more than >10% of participants in either randomization group are unevaluable, multiple imputation (MI) may be applied as described in section 6.7.
- (v) **Adjustment for Imbalances:** If key demographic variables or baseline characteristics related to decisional conflict differ substantively by study arm, we will use AIPW to adjust for these differences, as described in section 6.6

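### Covariates for the between-arm analyses are chosen by significance tests of baseline balance, which gives no narrower interval for decisional conflict and leaves the model open; a short prespecified list should replace the trigger

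*SAP*

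**What the plan says.** SAP 6.1 plans a comparison by arm of an open list of baseline features, seven of them named: "age, income, education, marital status, gestational age, perceived HIV risk, and experience of IPV". It sets the error level in the same paragraph, "Testing and confidence intervals (CIs) will be two-sided and at a 95% confidence level (i.e., alpha 0.05) with no adjustment for multiplicity", and ends with the covariate rule: "Any characteristics differing significantly by arm may be included as covariates in all analyses comparing study arms".

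Protocol 5.16 names eight features, adding parity: "age, income, education, marital status, gestational age, parity, perceived HIV risk, and experience of IPV". Its rule is firm but narrower: "Any characteristics differing significantly by arm will be included as covariates in sensitivity analyses comparing study arms". It otherwise leaves the primary analyses unadjusted.

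Three further provisions concern augmented inverse probability weighting (AIPW) for decisional conflict:

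- SAP 6.6 allows it as a post hoc sensitivity analysis: "This analysis will be exploratory in nature and will not replace the unadjusted primary analysis". It adds that the protocol is silent on chance imbalance, although Protocol 5.16 and 5.16.2 both deal with it.
- SAP 8.5(v), referring back to 6.6, is firmer: "If key demographic variables or baseline characteristics related to decisional conflict differ substantively by study arm, we will use AIPW to adjust".
- Protocol 5.16.2 has it take the place of the Welch test when demographic variables related to decisional conflict differ substantively by arm: "we will instead use augmented inverse probability weights (AIPW").

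Neither document names a fixed covariate list chosen because the features are expected to predict the outcome.

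**The concern.** Allocation is randomised 1:1 in permuted blocks, so a significant baseline difference between arms reflects chance. The test carries no information about whether the feature predicts decisional conflict. A rule built on it tends to admit irrelevant features and to pass over relevant ones that happen to be balanced.

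Two things are at stake. The SAP puts estimation and precision ahead of testing, and this rule does not deliver precision. Also, a permissive verb, an open feature list and a reach over all between-arm analyses let the model be settled after the arms have been compared. The DCS contrast is the only between-arm comparison in the SAP and is meant to inform a later efficacy trial. The protocol's version of the rule also reaches its exploratory comparison of retention with functional adherence.

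**Working it through.** **Inputs from the documents.** 50 women per arm; DCS standard deviation 13.26 in each arm (Protocol 5.15.1); two-sided alpha 0.05 without multiplicity adjustment (SAP 6.1); seven named features (SAP 6.1) or eight (Protocol 5.16). **Assumption.** The share of DCS variance explained by baseline features (R²) appears in neither document, so a range is used.

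**1. The plan's own figure.** Table 7 half-widths are t(0.975, n−1) × 13.26/√n. This gives 2.631 (n=100), 2.777 (n=90), 3.768 (n=50) and 3.984 (n=45), exactly as printed.

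**2. Unadjusted difference between arms.** 13.26 × √(2/50) = 2.652; t(0.975, 98) = 1.984; half-width 1.984 × 2.652 = 5.26. The simulated mean is 5.25.

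**3. How often chance fires the trigger.** With independent features, 1 − 0.95⁷ = 0.302 and 1 − 0.95⁸ = 0.337. Whatever the correlation, the probability cannot exceed 7 × 0.05 = 0.35 or 8 × 0.05 = 0.40.

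**4. What the trigger does to the interval.** Simulated trials with 50 per arm, seven independent normal features of which one is prognostic, no treatment effect, and 20,000 trials per row:

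| R² of the prognostic feature | Prognostic feature selected | Mean half-width, unadjusted | Mean half-width, significance-picked | Type I error, significance-picked |
|---|---|---|---|---|
| 0 | 4.8% | 5.25 | 5.30 | 4.5% |
| 0.1 | 5.2% | 5.25 | 5.29 | 4.9% |
| 0.3 | 5.0% | 5.25 | 5.26 | 4.2% |
| 0.5 | 4.8% | 5.25 | 5.23 | 3.5% |

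(In the first row no feature is prognostic; the selection rate is that of the feature holding that place.) The selection rate stays near 5% however strong the predictor. When nothing is prognostic and the rule fires, the mean half-width in those trials is 5.43 against 5.25. At R² of 0.3 to 0.5 the selected analysis lowers the empirical SD of the estimate by 3–6%, but the reported interval does not show it.

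**5. What a fixed list would do.** Eight independent covariates share the explained variance equally and four are prespecified, so the four capture half of the joint R². The approximate half-width is t(0.975, 94) × 2.652 × √(1 − R²/2) × √(97/93), where the last factor is the cost of estimating four covariates.

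| Joint R² of all eight | Formula | Simulated mean |
|---|---|---|
| 0.30 | 4.96 | 4.94 |
| 0.10 | 5.24 | 5.22 |
| 0.05 | 5.31 | 5.30 |
| 0 | 5.38 | 5.36 |

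In the same eight-covariate setting the significance-picked analysis gives 5.27 to 5.31. Against 5.25 unadjusted, the fixed list is about 6% narrower at R² = 0.30 (4.94/5.25 = 0.94) and about 2% wider at R² = 0 (5.36/5.25 = 1.02).

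**6. The rules side by side.**

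| Place | Trigger | Role of adjustment |
|---|---|---|
| SAP 6.1 | Significant difference by arm | Optional, in all between-arm analyses |
| Protocol 5.16 | Significant difference by arm | Required, sensitivity only |
| SAP 6.6 | Considerable imbalance | Optional, post hoc, does not replace unadjusted |
| SAP 8.5(v) | Substantive difference and related to DCS | Firm, as described in 6.6 |
| Protocol 5.16.2 | Substantive difference and related to DCS | Replaces the Welch test |

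All five depend on observed imbalance, none gives a covariate list fixed by prognosis, and the roles cannot all hold at once.

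**The case against.** The strongest reply is that little damage follows. Inclusion under SAP 6.1 is optional, SAP 8.5(iii) sets the DCS comparison as an unadjusted Welch test, SAP 6.6 says AIPW does not displace the unadjusted analysis, and Protocol 5.16 confines covariates to sensitivity analyses. The outcome is secondary in a 100-woman pilot, and the primary outcomes in the SAP are described in the intervention arm only. This stands. A reader might infer that the headline DCS estimate is already driven by chance imbalance; the documents do not support that. Only the substitution wording in Protocol 5.16.2 points that way, and it conflicts with SAP 6.6.

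A reader might also infer that every adjustment rule ignores prognosis. That is true of SAP 6.1 and Protocol 5.16, but SAP 8.5(v) and Protocol 5.16.2 also require a relation to decisional conflict.

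Nor does the rule tilt the result towards the intervention: simulated type I error stays at or below about 5%.

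Finally, a fixed list is not free. DCS is measured only after counselling, so there is no baseline score to adjust for. The listed features may explain little, in which case the fixed list is slightly worse than no adjustment. This stands too and limits the claim. It does not justify the significance trigger, which selects without regard to prognosis at any R².

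**Conclusion.** The point holds as a low-cost improvement, not as a threat to the trial's main conclusions. Selecting covariates by baseline significance responds to chance in roughly 30–34% of trials (independent features), finds a true predictor about 5% of the time, and leaves the reported half-width near 5.3 points against 5.25. It also leaves a modelling choice open after the arms are compared, and five provisions give conflicting accounts of when and how adjustment applies.

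It would go too far to say that prespecified adjustment would sharpen the main DCS result or can do no harm. The proposal below keeps the unadjusted comparison as the main result, so any gain falls on the sensitivity estimate. Its size depends on an R² that neither document gives. The simulations assume independent normal covariates and SD 13.26.

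**What to change.** - **SAP 6.1 and Protocol 5.16:** delete the significance trigger and describe baseline features by arm without tests.
- **Main analysis:** state in both documents that the unadjusted comparison is the main DCS result.
- **Sensitivity analysis:** before the arms are compared, name a short fixed list of expected predictors of decisional conflict and one adjusted model (linear or AIPW). Candidates among the features already listed are perceived HIV risk, age, education and gestational age, each used only if recorded before counselling.
- **SAP 6.6, SAP 8.5(v) and Protocol 5.16.2:** align them so that adjustment no longer depends on observed imbalance and AIPW does not take the place of the Welch test. Correct the statement in SAP 6.6 that the protocol does not address chance imbalance.

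The cost is wording in two documents and one additional model, with no new data. The downside is that the list must be chosen early. If its features prove weakly related to the outcome, the sensitivity interval will be about the same as the unadjusted one or slightly wider.
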